## **REVISED TEXT**

- 20. Part A (only cohorts with DTH challenge) only: Use of nicotine patches on the arm at screening that would interfere with the injection sites.
- 21. **Part A (only cohorts with DTH challenge) only:** Subjects participating, within seven days of screening, in recreational sun-bathing, or the use of a sun-bed, on the area of the skin from the wrist to the shoulder (inclusive).

## CHANGE 8

Amended text to allow screen failure data to be collected to meet the CONSORT requirements.

## Section 4.4 Screen and Baseline Failures

## DELETED TEXT

Data for screen and baseline failures will be collected in source documentation at the site but will not be transmitted to GSK.

## ADDED TEXT

Screen failures are defined as subjects who consent to participate in the clinical trial but are never subsequently randomized. In order to ensure transparent reporting of screen failure subjects, meet the Consolidated Standards of Reporting Trials (CONSORT) publishing requirements, and respond to queries from Regulatory authorities, a minimal set of screen failure information is required including, but

## not limited to, Demography, Screen Failure details, Eligibility Criteria, and any Serious Adverse Events.

## CHANGE 9

Change made to rectify an inconsistency in the protocol regarding the time when a vaccine may be given prior to the study start.

## Section 5.14.2.2 Prohibited Medications and Non-Drug Therapies, Part A and B

## **REVISED TEXT**

Live, attenuated or recombinant vaccine(s) within one month of screening Day 1 and until completion of the follow up visit.

## CHANGE 10

Blood volume increased to allow for extra blood tests due to pre-existing ADA screening and any repeated tests required. As the study takes place over a long duration this is not perceived to be a safety risk.

## Section 6 Study Assessments and Procedures

## **REVISED TEXT**

No more than  $\frac{500}{600}$  mL of blood will be collected over the duration of the study, including any extra assessments that may be required.

Inclusion of a sample for pre-existing ADA testing.

## Section 6.1 Time and Events Table, Table 6

## **REVISED TEXT**

Protocol Activity	Screening	Follow Up	Surveilla	nce Visit
	Up to 30 Days prior to Day 1	Week X ^a	6 months⁵	12 months
Immunogenicity Sample	X	Х		

## CHANGE 12

Inclusion of *in vitro* LAG-3+ activity blood test. Also added footnote to confirm when weight should be measured to calculate dose required.

## Section 6.1 Time and Events Table, Table 7

## ADDED TEXT

Protoco I Activity	Base -line		In Clinic Period Out Patient Visits														
			Day 1 Day 2 Day 3 Day 4 Day														
	Day - 1	Pre- dos e		post-	post- infusio	post- infusio	post- infusio	24 hour post- infusio n start	post- infusio	post- infusio	nour	у	Da y 15	Da y 18	у	Da y 25ª	у
In vitro LAG-3+ activity		X		X							X						

## ADDED TEXT

## i. To calculate the correct dose, weight must be measured on Day -1 or Day 1 pre-dose.

## CHANGE 13

Inclusion of *in vitro* LAG-3+ activity blood test and time window on Day 28. Also added footnote to confirm when weight should be measured to calculate dose required.

## Section 6.1 Time and Events Table, Table 8

## ADDED TEXT

Protocol Activity	-	st lenge	In Clinic Period										Out Patient Visits										
			Day 28							Day 30 (Day 2 post-	Day 31 (Day 3 post-	Day 32 (Day 4 post-											
										dose)	dose)	dose)											
	Day 1	Day 3			0 hour	2 hour post- infusion start	4 hour post- infusion start	6 hour post- infusion start	post-	post-	48 hours post- infusion start	post- infusion start	(Day 8 post-	11 post-		`18 [°] post-		Day 53 (Day 25 post- dose)	29 post-	(Day 43 post-		(Day 85 post-	Day 149 (Day 121 post- dose)
Window			- /+3d										-/+1d	-/+1d	-/+1d	-/+1d	-/+1d	-/+1d	-/+1d	-/+2d	-/+2d	-/+2d	-/+3d
In vitro LAG-3+ activity				X		X							X										

## ADDED TEXT

## n. To calculate the correct dose, weight must be measured on Day 28 or Day 29 pre-dose.

## CHANGE 14

Inclusion of *in vitro* LAG-3+ activity blood test. Also added footnote to confirm when weight should be measured to calculate dose required.

## Section 6.1 Time and Events Table, Table 9

## ADDED TEXT

Protocol Activity	Base- line		In Clinic Period							Out Patient Visits											
			Day 1					Day 2	Day 3	Day 4	Day 8										
	Day -1	Pre- dose	0 hour	2 hour post- infusion start	post-	post-	post-	post-	post-	72 hour post- infusion start	post-	Day 11	Day 15	Day 18	Day 22	Day 25	Day 29	Day 43	Day 57	Day 85	Day 121
In vitro LAG-3+ activity		X		x							X										

## ADDED TEXT

j. To calculate the correct dose, weight must be measured on Day -1 or Day 1 pre-dose.

Included a blood test for serum tryptase if a suspected acute hypersensitivity reaction occurs.

## Section 6.3.4 Infusion-related Reactions and Hypersensitivity Reactions, 2nd paragraph

## ADDED TEXT

## In the event of a suspected acute hypersensitivity reaction a blood sample should be taken between 30minutes – 3 hours of the event for serum tryptase analysis.

## CHANGE 16

Added further information regarding the ADA testing.

## Section 6.7.1 Immunogenicity, Blood Sample Collection

## ADDED TEXT

## In Parts A and B, only subjects with a negative pre-existing ADA status at screening will be included.

## Section 6.7.1 Immunogenicity, Sample Analysis

## **REVISED TEXT**

Samples will be analyzed for the presence of anti-GSK2831781 antibodies using a validated immunoelectrochemiluminescent (ECL) assays. The assay involves screening. confirmation and titration steps (tiered-testing approach). Immunogenicity assays will be performed by Clinical Immunology, GSK. ADAs to GSK2831781 will be detected using a validated bridging electrochemiluminescent (ECL) immunoassay. This assay will be used both to prospectively define subjects' pre-existing ADA status and to evaluate post-dose ADA responses. The bioanalytical cut points of screening and confirmation for a positive antibody response will be determined statistically during ADA assay validation from drug-naive human serum samples. Samples will be directly tested in confirmatory ADA assay to define subjects' preexisting ADA status for subject screening if required. An ADA assay involving screening, confirmation and titration steps (tiered-testing approach) will be adopted for study samples. Confirmed positive samples will be titrated to obtain the titre of the anti-GSK2831781 antibodies. Further antibody characterization may be performed, if needed. Results will be reported at the end of the study. Samples testing positive for anti-GSK2831781 antibodies may be further characterized for the presence of GSK2831781 neutralising activity (NAb) using a validated ADCC reporter gene assay, if needed. Details on sample preparation, storage and analysis will be given in the SPM.

Added section relating to the *in vitro* LAG-3+ activity assay.

## Section 6.8.7 In Vitro LAG-3+ activity

## ADDED TEXT

The functional activity of GSK2831781 to bind to LAG-3+ cells and induce Fc gamma receptor 3A signalling may be assessed using the Fc gamma 3A reporter cell assay

CHANGE 18

Changed volume of blood required for PGx due to change in guidelines.

## Section 12.2 Pharmacogenetic Research, Study Assessments and Procedures, 2nd paragraph

## **REVISED TEXT**

In addition to any blood samples taken for the clinical study, a whole blood sample ( $\sim 106$  ml) will be collected for the PGx research using a tube containing EDTA.

## **AMENDMENT 1**

## Summary of Amendment Changes with Rationale

This amendment is to address the queries raised by the MHRA.

The opportunity has been taken to make some minor administrative changes.

## List of Specific Changes

CHANGE 1

Incorrect doses removed from Follow-up box.

## Section 3.1 Study Schematic, Healthy Volunteers (DTH) schematic

**REVISED TEXT** 

Follow Up (See Table 1) +6 (0.003, 0.0015, 0.0075 and 0.04mg/kg cohorts only) and 12 month surveillance visit

## CHANGE 2

Change made to address comment from MHRA.

## Table 1 Dose escalation/Cohort Structure and Safety review periods, 8th row.

**REVISED TEXT** 

Planned Doses	Number of subjects (active:placebo)	Safety Follow-up period to progress to next subjects/cohorts	PPD DTH Challenge if Healthy volunteer/ Biopsy if patient	Follow-up and end of exclusion of systemic immunosuppressives				
Healthy Volunte	eers							
0.0003mg/kg	1:1	1:1 wait 28 days post- dose	No DTH	Day 29 ± 1 day (28 days post-dosing)				
0.0015mg/kg				Day 43 ± 1 day (42 days post-dosing)				
0.0075mg/kg	6:3	1:1 wait 48 hours post-dose	DTH	Day 113 ± 2 days (84 days post-dosing)				
0.04mg/kg		5:2 wait 28 days post- dose		Day 175 ± 3 days (146 days post-dosing)				
0.15mg/kg	-			Day 219 ± 7 days (190 days post-dosing)				
			on emerging exposur	e or earlier reduction in DTH				

## CHANGE 3

Allowance of a phone call to replace the 12 month visit has been removed as per MHRA request. Clarification of why additional 6 month surveillance visit for 0.15mg/kg cohort is not required, as per MHRA request. Removal of incorrect doses from text in 'Healthy volunteers with DTH' paragraph.

## Section 3.2 Study Design Detail

## REVISED TEXT

## Healthy volunteers without DTH

All subjects will attend a surveillance visit at 6 and 12 months (a telephone call is permitted for the 12 month visit if required).

## **REVISED TEXT**

## Healthy volunteers with DTH

All subjects in the 0.003, 0.0015, 0.0075 and the 0.04mg/kg cohorts will attend a surveillance visit at 6 months and 12 months (a telephone call is permitted for the 12 month visit if required). As the follow-up visit is at approximately 6 months (190 days post-dose, as per Table 1), subjects in the 0.15mg/kg cohort do not require an additional post-dose surveillance visit at 6 months and will only attend a surveillance visit at 12 months (a telephone call is permitted for the 12 month visit if required).

## CHANGE 4

Change made to address comment from MHRA.

## Section 3.2.1 Healthy Volunteer to Patient Switching, 2nd paragraph

## REVISED TEXT

If a dose switch occurs earlier than 0.15mg/kg, extra cohorts would be added at the lower doses for psoriasis patients so that the starting dose is the same as the last dose used in healthy volunteers. When the decision to switch to psoriasis patients is made, no further dosing of healthy volunteers will occur. If the understanding of EC50 for LAG-3+ T cells depletion change and/or emerging PK profiles differs markedly from prediction, the maximum dose for healthy volunteers may also change. If GSK2831781 exposure is substantially less than predicted the maximum dose into healthy subjects would be increased to a dose predicted by the emerging pharmacokinetic data to provide a similar exposure as currently predicted at 0.15mg/kg (i.e. a target AUC of ~1800µg*h/mL (See Table 2). If a dose switch then occurs later, psoriasis cohorts would start at the last dose used in healthy volunteers. Details of dose adjustment can be found in Section 5.4.

## CHANGE 5

Change made for clarity as per MHRA request.

## Section 3.3.1 Design Rationale, 5th paragraph, 2nd sentence

## **REVISED TEXT**

This dose of 0.15 mg/kg might be altered if emerging PK profiles differ markedly from predictions (See Section 3.2.1).

## CHANGE 6

Change made for clarity as per MHRA request.

## Section 3.3.2.3 Assessment of GSK2831781 pharmacology in healthy volunteers, 5th paragraph

## **REVISED TEXT**

However, reduction of the DTH response could occur at a lower or higher dose. Therefore, the decisions to switch to psoriasis patients will be based on demonstration of reduction of the DTH response but with a maximum dose for healthy subjects of 0.15mg/kg (dose could be altered dependent on emerging PK data and/or PD data), to limit the duration of exposure above the *in vitro* EC50 ADCC killing activity (where there are lifestyle and medication restrictions), to no more than approximately 6 months (See Section 3.2.1 and Section 5.4 Planned Dose Adjustments).

CHANGE 7

Change made for clarity as per MHRA request.

## Section 5.4 Planned Dose Adjustments, 3rd paragraph, last sentence

## **REVISED TEXT**

If emerging PK data departs from prediction, outcomes may also include continuing dose escalation in healthy volunteers beyond the maximum of 0.15mg/kg up to a maximum duration of exposure above EC50 of approximately 6 months, if there are no other safety/tolerability findings or reduction of DTH response (See Section 3.2.1).

## CHANGE 8

Change made to address comment from MHRA.

## Section 5.5 Dose Adjustment/Stopping/Monitoring Criteria, 1st and 2nd paragraphs

## **REVISED TEXT**

If one or more subject experiences an Serious Adverse Event (SAE) that can be reasonably attributed to GSK2831781, the dose escalation will be temporarily halted and no further subject will be dosed until a full safety review of the data has taken place. Relevant reporting and discussion with the DEC, (which must include the GSK medical monitor), relevant GSK personnel, and with the Ethics Committee and Regulatory

Agency will then take place prior to any resumption of dosing. If following the safety review a decision is made to restart dose escalation, this may be allowed after approval of a substantial amendment.

If two or more subjects experience a severe or significant non-serious AE that can be reasonably attributed to GSK2831781, the dose escalation will be temporarily halted and no further subject will be dosed until a full safety review of the study has taken place. Relevant reporting and discussion with the DEC (which must include the GSK medical monitor), relevant GSK personnel, and with the Ethics Committee and Regulatory Agency will then take place prior to any resumption of dosing. If following the safety review a decision is made to restart dose escalation, this may be allowed after approval of a substantial amendment.

## CHANGE 9

Change made to address comment from MHRA.

## Section 5.5 Dose Adjustment/Stopping/Monitoring Criteria

## **REVISED TEXT**

- 22. Neutropenia (the following must be confirmed by repeat samples):
  - If one subject experiences neutrophil count < 1.5 x 109/L for >7 days for the first 28 days for the first 2 healthy volunteer cohorts.
  - If one or more subjects experiences neutrophil count  $<0.5 \times 10^9/L$  for >7 days

## CHANGE 10

Allowance of a phone call to replace the 12 month visit has been removed as per MHRA request.

## Section 6.1 Time and Events Table, Table 6 Footnote c.

DELETED TEXT

c. A telephone call is permitted for healthy volunteers only, if required.

Correction to demographic parameters being collected.

## Section 6.2 Demographic/Medical History Assessments, 1st paragraph

## **REVISED TEXT**

The following demographic parameters will be captured: date year of birth, gender, race and ethnicity.

## CHANGE 12

Removal of viral testing parameters from screening list for consistency with Time and Events table. These tests are taken at baseline and are reflected in the baseline tests list.

## Section 6.3.7 Clinical Laboratory Assessments, Other screening tests, 6th row

**REVISED TEXT** 

#### Other screening tests

HIV
Hepatitis B (HBsAg)
Hepatitis C (Hep C antibody)
FSH and estradiol (as needed in women of non-child bearing potential only)
Alcohol and drug screen (to include at minimum: amphetamines, barbiturates, cocaine, opiates,
cannabinoids and benzodiazepines).
CMV, EBV, HSV, VZV
Thyroid Function Test
Quantiferon test

1. INTRODUCTION

The purpose of this reporting and analysis plan (RAP) is to describe the analyses to be included in the Clinical Study Report for Protocol

1.1. RAP Amendments

Revision chronology:

RAP Section	Amendment Details			
Reporting and Analysis Plan_Study200630_Final_V1 [7-Nov-2017]				
Reporting and Analysis Pla	Reporting and Analysis Plan_Study200630_Amendment_Final_V1 [23-Jan-2018]			
Soluble LAG3 concentrations	Change from free and complex sLAG-3 to total sLAG-3			
Transcriptomics	Analyses included			
PK / PD Dataset Specification	Details removed as per current TMF guidelines, the specifications for these datasets will need to be in a separate document, which will reside in eTMF.			
Minor updates	 Clarification of some outputs Added details for the Bayesian analyses Separate sections/outputs for IHC parameters and epidermis thickness Categories for ECG to match the protocol 			

2. SUMMARY OF KEY PROTOCOL INFORMATION

2.1. Changes to the Protocol Defined Statistical Analysis Plan

Changes from the originally planned statistical analysis specified in the protocol are outlined in Table 1.

Table 1 Changes to Protocol Defined Analysis Plan

Protocol	Reporting & Analysis Plan		
Statistical Analysis Plan	Statistical Analysis Plan	Rationale for Changes	
PK parameters to be derived include AUC(0-week4), Vss and MRT	 PK parameters AUC(0- week4), Vss and MRT will not be derived 	These parameters are not relevant for the study/program and/or a monoclonal antibody	
Dose proportionality will be assessed using the power model	No statistical analysis (e.g. using a power model) will be performed	Interim analyses to support DEC meetings showed that the PK data is clearly non-linear (less than proportional increase in exposure with increasing dose), and hence a statistical analysis to test dose proportionality is redundant	
Effect on free and GSK2831781 bound sLAG-3 concentrations	Total sLAG-3 concentrations will be used instead of free and complex sLAG-3	The assays for free and complex sLAG-3 are not quantitative, and therefore a new assay to measure total sLAG-3 was developed. PK/PD modelling will be used to investigate the time course of	

CONFIDENTIAL

[figure not shown]
Protocol	Reporting & Analysis Plan	
Statistical Analysis Plan	Statistical Analysis Plan Rationale for Changes	
		free and complex sLAG-3.

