In Part B, psoriasis patients will be assessed for clinical response to determine long term effect up to Day 121. Emerging pharmacokinetic data from subjects in Part A and in Part B (0.5 and 1.5mg/kg dose cohort) demonstrated a much more rapid clearance of GSK2831781 than previously predicted (see Figure 1 and Table 1). At the highest dose delivered (5mg/kg), levels of GSK2831781 are expected to be below the lower limit of quantitation by Day 85. Subjects in Part B receiving 1.5mg/kg and 5.0mg/kg will therefore have a combined final follow-up and surveillance visit at 6 months (183 days \pm 7). If a follow-up visit has already taken place, a final surveillance telephone call will take place as soon as practically possible after the introduction of Amendment 10 (see Table 1). Lifestyle and medication restrictions are not mandated between the follow-up visit and final long-term surveillance visit, but use of any immunosuppressant or experimental medicine during this time, will be assessed for likelihood of confounding results. Subjects with abnormalities at the final study visit that can be reasonably attributed to GSK2831781, will be asked to return for continued surveillance visits until the abnormality has resolved or is no longer clinically significant.

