Dose (mg/kg)	Cmax (µg/mL)	AUC (µg*h/mL)	Dose ratio	Cmax ratio	AUC ratio		Cmax (µg/m L)	AUC (µg*h/ mL)
0.0003	0.00763	3.61	100000x	171791x	36802x	0.908x	NA	NA
0.0015	0.0381	18.1	20000x	34358x	7360x	4.54x	NA	NA
0.0075	0.191	90.3	4000x	6872x	1472x	22.7x	0.152	1.38
0.04	1.02	482	750x	1288x	276x	121x	0.861	25.4
0.15	3.81	1807	200x	344x	73.6x	454x	3.22	208
0.5	12.7	6023	60x	103x	22.1x	1514x	8.48	903
1.5	38.1	18069	20x	34.4x	7.4x	4541x	40.1	8250
5	127	60232	6.0x	10.3x	2.2x	15136x	95.6†	30700†

* EC50 = 8.4 ng/mL for depletion of LAG-3 + cells in human plasma

[figure not shown]
** For doses up to and including 1.5mg/kg calculations are based on actual PK interim data from dose escalation meetings (all concentrations, except for one, were below LLOQ of 10ng/mL after 0.0003 and 0.0015mg/kg, and therefore PK parameters could not be derived). For 5mg/kg dose: Cmax and AUC shown are predicted using a population PK model that was developed with data from 0.0075-1.5mg/kg GSK2831781

† Predicted values

b)

Note: symbols are actual subject PK measurements observed during the study. Lines represent median drug concentrations per cohort based on the model predictions, and the shaded areas indicate the 95% confidence intervals of the model predications.

3.3.2.2. Starting dose determination (Minimum Anticipated Biologically Effective Level [MABEL] approach)

In order to investigate the pharmacology aspect of GSK2831781, predicted receptor occupancy (RO) in the plasma of healthy subjects, based on the binding affinity of the drug for its target and LAG-3 receptor concentration in the blood (Ganusov *et al*, 2007) at the predicted Cmax (assuming no target mediated disposition and in the absence of soluble LAG-3) of the proposed doses, were estimated and summarised in Table 3 below.

Dose (mg/kg)	Cmax (µg/mL)	RO
0.0003	0.00763	19%
0.0015	0.0381	54%
0.0075	0.191	86%
0.04	1.02	97%
0.15	3.81	99%
0.5	12.7	100%
1.5	38.1	100%
5	127	100%

Table 3Predicted receptor occupancy in the plasma at Cmax of the
proposed GSK2831781 doses

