9. DATA ANALYSIS AND STATISTICAL CONSIDERATIONS

9.1. Hypotheses and Treatment Comparisons

The primary objective is to determine the safety and tolerability of single IV Doses of GSK2831781 in healthy volunteers and in patients with mild to moderate psoriasis.

There are no formal hypotheses planned.

An assessment of dose proportionality of AUC and Cmax, following single dosing, will be conducted separately for healthy volunteers and patients with psoriasis.

Where appropriate, an estimation approach will be used to address the study objectives where point estimates and corresponding confidence intervals will be constructed to provide a plausible range of values for the comparison of interest.

Exploratory comparisons will be conducted to investigate the effect of ADA status at baseline on the pharmacokinetics of GSK2831781.

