9.3.1. Interim Analysis

Dependant on the dose cohorts reached in the escalation, formal interim analyses may be performed after the last subject in the Healthy Volunteer DTH cohort has completed their 4 week post dose assessment visit, and also after the last subject in the Psoriasis group has completed the final PK assessment visit, to inform internal development decisions. If required, additional interim analyses to contribute to internal development decisions may also be performed during Part B (psoriasis cohorts). Full details of interim analysis will be documented in a RAP addendum.

For Parts A and B of the study, review of safety, tolerability, available pharmacokinetic and DTH induration for healthy volunteers or PASI and PLSS for psoriasis patients will be performed by DEC to aid decisions to proceed to higher dose strengths or, between cohorts 5 and 6 to subjects with pre-existing ADA. This analysis can include review of individual subject data, summaries, graphical presentations and/or statistical analysis. Owing to the modest time intervals involved, all data to be used for dose escalation decisions will be preliminary, non-quality-controlled (non-QC'ed), data.

Safety/tolerability data monitoring and the decision to proceed to the next dose level of GSK2831781 will be made by the DEC (see Section 5.4 for more details).

The GSK Clinical Pharmacology Modeling and Simulation (CPMS) representative will extract PK data (including treatment information) from SMS2000 using unscrambled subject IDs. PK data will provide supporting evidence for each dose modification decision. Importantly, if the emerging PK data is significantly different from the predicted values, adjustment may have to be made to the planned doses (see Section 5.4). Dose modification decisions will take into account the emerging PK data, new PK prediction for the next dose and thus the expected safety cover for the next dose.

Standard Pharmacokinetic parameters will be derived for each subject by the GSK CPMS representative when possible. These parameters will be summarised by planned dose.

The criteria for switching from healthy volunteers to psoriasis patients are outlined in Section 3.2.1.

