Separately for Parts A and B, dose proportionality across the single dose cohorts of \log_{e^-} transformed parameters AUC(0- ∞) (or if not available AUC(0-t)) and Cmax will be assessed using the power model for of data permit, as described below:

 $y = \alpha * dose^{\beta}$

where y denotes the PK parameter being analysed and α depends on subject. Dose proportionality implies that β =1 and will be assessed by estimating β along with its confidence interval. The exponent, β , in the power model will be estimated by regressing the log_e-transformed PK parameter on log_e dose:

 $\log(y) = \log(\alpha) + \beta * \log(\text{dose})$

The power model will be fitted by restricted maximum likelihood (REML), for all groups across the single dose cohorts. Both the intercept and slope will be fitted as random effects. If this model fails to converge, the model will be refitted with slope as a fixed effect. If the mixed effects model does not converge then a fixed effects power model will be fitted. The slope will be estimated from the power model and the corresponding 90% confidence interval calculated.

If the log transformed models are not proportional and sufficient data are available, loge transformed dose-normalised AUC($0-\infty$) (or if not available AUC(0-t)) and Cmax will be analysed using a suitable mixed effects model, fitting regimen as a fixed effect and subject as a random effect. Point estimates and corresponding 90% confidence intervals for the ratios of each dose level to the reference dose will be determined.

All other data will be summarised and listed.

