14.7.2. Pharmacokinetic / Pharmacodynamic Methodology

An exploratory graphical analysis of the data will be performed by generating the plots as presented in Appendix 9.

Model development will be data driven.

The initial PK model of choice will be a compartmental model with linear and nonlinear drug elimination. Further model testing will include, but it is not limited to, a compartmental model with target mediated drug disposition (TMDD) and a minimal PBPK model with TMDD incorporated. We anticipate TMDD to be driven by soluble LAG3 (sLAG3). However, if data allow, we plan to test also more complex models with TMDD driven by both, sLAG3 and T-cell bound LAG3.

The final PK model, possibly incorporating TMDD, will be used to develop a PK-RO model. Data relative to CD4+CD45RA- cell count will be used to model RO (quantified by J11L1 marker) and T-cell depletion (quantified by 1B4 marker). The initial RO model will likely be an Emax model. More complex models might be investigated if the data support it.

If plots (and summary) of NCA derived PK parameters identified ADA status, and/or HV vs Pso as possible significant covariates, we will investigate the influence of these covariates in the PK and RO models. Other covariates may be explored as appropriate.

CONFIDENTIAL

200630

Model acceptability will be judged by convergence, covariance estimation and standard goodness-of-fit plots that may include, but are not limited to:

- Population and individual predictions versus observations
- Conditional weighted residuals versus population predictions and time

For the final PK and the final RO models visual predictive checks (VPCs) will be conducted to assess graphically whether simulations from the developed models are able to reproduce both the central trend and variability in the observed data from the current study as a function of time.

The VPC will be based on 1000 simulations with the model and the design structure of the observed data (i.e. dose level and time, time of PK sampling and individual values of model covariates, if any). The median and the 10th and 90th will be compared to the observed data. Stratification by dose level of GSK2831781 will be used. Other stratification, such as healthy/ psoriasis will be applied in case these covariates were tested in the model.

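### The SAP drops the dose-proportionality analysis because exposure rose less than proportionally, but the protocol's interim data show AUC rising more than proportionally at every observed step

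*SAP*

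**What the plan says.** Protocol section 9.1 commits to the analysis: "An assessment of dose proportionality of AUC and Cmax, following single dosing, will be conducted separately for healthy volunteers and patients with psoriasis". Section 9.3.2.2 gives the method. A power model is fitted separately for Parts A and B; an exponent of 1 means proportional, and the exponent is reported with a 90% confidence interval. The fallback for a fitting failure is stated: "If the mixed effects model does not converge then a fixed effects power model will be fitted". There is also a next step if proportionality fails: "If the log transformed models are not proportional and sufficient data are available", dose-normalised AUC and Cmax are to be compared with a reference dose, as ratios with 90% confidence intervals.

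SAP section 2.1, Table 1 replaces all of this with no statistical analysis. The reason given is that interim analyses for the dose escalation meetings showed that "the PK data is clearly non-linear (less than proportional increase in exposure with increasing dose", which is said to make a test redundant.

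Protocol section 3.3.2.1, Table 2 lists interim exposures by dose. Its footnote states: "For doses up to and including 1.5mg/kg calculations are based on actual PK interim data from dose escalation meetings". The 5 mg/kg entry is a population PK prediction.

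**The concern.** The SAP and Table 2 appear to rest on the same interim data, yet they disagree on direction. A less than proportional rise means an exponent below 1, with apparent clearance increasing as dose increases. In Table 2, apparent clearance falls at each dose.

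The SAP's modelling plan also fits Table 2 better than it fits the stated reason: "The initial PK model of choice will be a compartmental model with linear and nonlinear drug elimination". Elimination that saturates gives a more than proportional rise in AUC.

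Two things are at stake. The recorded reason for departing from the protocol would tell a reader that exposure grows more slowly than dose when AUC does the opposite, in a first-in-human study whose interim results are meant to inform later studies. And a planned estimate with its interval is lost, although the protocol treats non-proportionality as the trigger for further estimation rather than a reason to stop.

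**Working it through.** **Reading of Table 2.** The original linear prediction is AUC = dose × 70 kg / CL, with CL = 0.00581 L/h (protocol section 3.3.2.1). At 0.15 mg/kg this is 0.15 × 70 / 0.00581 = 1807 µg·h/mL, as tabulated. All eight predicted AUCs reproduce within 0.2%, so the columns are read correctly.

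**Direction.** The inputs are the observed Cmax and AUC in Table 2. The step exponent is ln(AUC₂/AUC₁) / ln(dose₂/dose₁); for the first step, ln(18.4)/ln(5.33) = 1.74.

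| Dose (mg/kg) | AUC (µg·h/mL) | AUC per mg/kg | Dose/AUC (mL/h/kg) | AUC as % of linear prediction | AUC step exponent | Cmax step exponent |
|---|---|---|---|---|---|---|
| 0.0075 | 1.38 | 184 | 5.43 | 1.5 | – | – |
| 0.04 | 25.4 | 635 | 1.57 | 5.3 | 1.74 | 1.04 |
| 0.15 | 208 | 1387 | 0.72 | 11.5 | 1.59 | 1.00 |
| 0.5 (patients) | 903 | 1806 | 0.55 | 15.0 | 1.22 | 0.80 |
| 1.5 (patients) | 8250 | 5500 | 0.18 | 45.7 | 2.01 | 1.41 |

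Overall, dose rises 1.5/0.0075 = 200-fold and AUC 8250/1.38 = 5,978-fold. The log-log AUC slope is 1.68 in Part A (three doses), 2.01 for the one observed Part B pair, 1.60 over all five doses and 1.55 without the lowest. The Cmax slope over all five doses is 1.02. The predicted 5 mg/kg AUC (30700) gives a step exponent of 1.09; nothing here depends on it.

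**If Table 2 reports AUC(0-t).** Truncation at the 10 ng/mL assay limit shortens low-dose AUCs most. Add a tail of 0.01 µg/mL × t½/ln 2 to each AUC, with t½ assumed to be 2 to 23 days (23 is the protocol's own prediction).

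- At 2 days the tail is 0.69 µg·h/mL. The Part A slope is 1.54 and the pooled slope 1.53.
- At 23 days the tail is 7.96 µg·h/mL. The Part A slope is 1.04 and the pooled slope 1.27. The lowest step reverses (AUC per mg/kg 1246, then 834; exponent 0.76). The other three steps stay at 1.41, 1.20 and 2.01.

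**Sparse sampling at 0.5 mg/kg.** If concentrations only decline after the infusion, the area missed in the gap after the last quantifiable sample is at most AUC × gap/tlast. On the protocol Table 10 schedule the worst gap is 72 h to 168 h, so the true AUC is at most 1 + 96/72 = 2.33 times the reported one. Proportionality from 0.5 to 1.5 mg/kg would need 8250/3 = 2750, which is 3.05 times 903. At the bound the exponent is ln(8250/2107)/ln 3 = 1.24. With the visit a day late (192 h), the bound is 2.67 and the exponent 1.12.

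**Precision if the analysis is restored.** The 90% half-width for the exponent is t(0.95, n−2) × σ / √Sxx, with σ² = ln(1 + CV²), Sxx the sum of squares of log dose, and an assumed between-subject CV of 30% to 60% (σ = 0.294 to 0.555).

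- Part A: 6 + 6 + 12 = 24 active subjects at the three doses with derivable PK; Sxx = 36.4; half-width 0.08 to 0.16.
- Part B: 18 active subjects; Sxx = 15.9; half-width 0.13 to 0.24.

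**The case against.** The strongest reply is that the operative reason survives: the PK is non-linear whichever way it bends, so a wrong descriptor in brackets does not undo the decision to skip a test. It is true that non-linearity stands. But the protocol planned estimation, not only a test, and it asks for dose-normalised ratios precisely when proportionality fails and data suffice.

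Second, little is lost. SAP section 14.4.3 and Tables 4.5 and 4.6 still give geometric means with 95% confidence intervals by dose, Figures 4.5 and 4.6 plot parameters against dose, and nonlinear modelling is planned. This limits the harm. It does not supply between-dose ratios with intervals, or correct the stated reason.

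Third, the exponents vary from step to step, so one power-model slope describes the data poorly. That is fair, and it favours the ratios over a single exponent.

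Fourth, the evidence is thin. The protocol says "all data to be used for dose escalation decisions will be preliminary"; there is one value per cohort; the 0.15 mg/kg dose was given to two cohorts that differ in ADA status, and the table does not say which its value reflects; and the 0.15 to 0.5 mg/kg step crosses from volunteers to patients. With the 23-day tail, the Part A slope of 1.04 cannot be told from 1. That is the extreme case, because the protocol reports that emerging data "demonstrated a much more rapid clearance of GSK2831781 than previously predicted". The weaknesses apply equally to the SAP, which calls the same kind of data clear.

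Fifth, the SAP does not cite Table 2 and does not define exposure. A shared source is likely from the footnote but is not proven. Reading exposure as Cmax does not rescue the wording: the overall slope is 1.02, and the one observed step clearly below 1 (0.80) is followed by 1.41.

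**Conclusion.** The concern holds. For AUC, the stated direction is contradicted by all four observed steps in protocol Table 2 and within each part taken separately. For Cmax it is unsupported.

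The upper three steps keep exponents above 1 under the assay-limit check, and the 0.5 to 1.5 mg/kg step also stays above 1 under the sampling-gap check, at 1.12 or more. The size of the Part A slope is less secure: it lies between 1.04 and 1.68, depending on the AUC type and the assumed half-life. The conclusion rests on cohort-level, non-QC'd values, and no confidence interval can be computed from them.

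AUC was below the linear prediction at every dose (1.5% to 45.7%), so lower than predicted may have been written as less than proportional. That is a possible explanation, not an established one.

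The consequence is moderate. Readers can still see the trend from the planned outputs, but the documented reason for a protocol change is wrong for AUC and a planned estimate is missing. It should be fixed.

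**What to change.** 1. In SAP Table 1, reconcile the reason with protocol Table 2: state a more than proportional increase in AUC, subject to the final data, and describe Cmax separately from the final data.
2. For Parts A and B separately, report dose-normalised AUC and Cmax ratios to a named reference dose, with 90% confidence intervals. State which AUC is used.
3. Optionally add the power-model exponent with its 90% interval, using the protocol's fixed-effects version. Each subject has one dose, so random subject slopes cannot be estimated. Say that one exponent is only a summary if the slope changes with dose, and that the planned nonlinear model describes the shape.

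The cost is one wording correction and one small table from parameters already being derived. The drawback is that a single exponent, if shown, may be read as more than a summary.
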